3. BACKGROUND

a. Past Experimental and/or Clinical Findings

Fosaprepitant is a very effective medication used to prevent post-operative nausea and vomiting in patients having surgery under general anesthesia. The mechanism of action

of this medication is through substance P inhibition, which has effects on numerous sensory systems in the brain and spinal column. In patients who have surgery under general anesthesia with intraoperative neuromonitoring, the sensory and motor pathways are monitored throughout the surgical procedure. It is not known if fosaprepitant could interfere with these intraoperative neuromonitoring signals due to its effect on sensory pathways via substance P inhibition.

b. Findings from Past Animal Experiments

No relevant animal literature exists.

4. RADIOISOTOPES OR RADIATION MACHINES

N/A

5. DEVICES USED IN THE STUDY

N/A

6. DRUGS, BIOLOGICS, REAGENTS, OR CHEMICALS USED IN THE STUDY

a. Investigational Drugs, Biologics, Reagents, or Chemicals

N/A

b. Commercial Drugs, Biologics, Reagents, or Chemicals

Commercial Product 1	
Name:	Fosaprepitant
Dosage:	150 mg
Administration Route	Intravenous (i.v.)
New and different use? (Y/N)	No

7. DISINFECTION PROCEDURES FOR MEDICAL EQUIPMENT USED ON BOTH HUMANS AND ANIMALS

N/A

8. PARTICIPANT POPULATION

a. Planned Enrollment

The total number of participants expected to enroll is 50.

Patients presenting for surgery under general anesthesia with intraoperative neuromonitoring will be approached to participant in this study.

All participants will be at Stanford University Medical Center.

We selected this patient population because we are particularly interested in knowing what effects, if any, fosaprepitant has on intraoperative neuromonitoring signals in patients having surgery under general anesthesia.

b. Age, Gender, and Ethnic Background

There are no exclusions or preferences based on age, gender, or ethnic background.

c. Vulnerable Populations

We are not specifically seeking out any potentially vulnerable populations.

d. Rationale for Exclusion of Certain Populations

No children will be enrolled because this study will be carried out at Stanford University Medical Center which only manages adult patients.

e. Stanford Populations

Enrollment of laboratory personnel, employees, and/or students would be purely coincidental. No payment will be provided for participation.

f. Healthy Volunteers

No healthy volunteers will be enrolled in this study. Only patients coming to Stanford University Medical Center for surgery requiring general anesthesia and intraoperative neuromonitoring will be approached to participate.

g. Recruitment Details

Patients coming to Stanford University Medical Center for surgery requiring general anesthesia and intraoperative neuromonitoring will be approached to participate.

h. Eligibility Criteria**i. Inclusion Criteria**

Patients presenting to Stanford University Medical Center for surgery requiring general anesthesia with intraoperative neuromonitoring will be approached to participate.

ii. Exclusion Criteria

Exclusion criteria include patient refusal or inability to consent to this study, or a contraindication to receiving fosaprepitant.

i. Screening Procedures

Medical chart reviewed by the anesthesiologists involved in the study.

j. Participation in Multiple Protocols

Patients will be asked about participation in other studies. Enrollment in other studies that don't interfere with this study is acceptable. Surgical patients are frequently asked by the surgeon to allow the collection of tissue samples for research purposes. This is done during surgery and does not in any way interfere with this study.

k. Payments to Participants

Subjects will not receive payment.

l. Costs to Participants

None. This medication available on the Stanford University Medical Center operating rooms formulary. It can be used at the discretion of the anesthesiologist managing the case.

m. Planned Duration of the Study

One year. The total time requirement for each participant is minimal. It includes the time to get informed consent.

9. RISKS

a. Potential Risks**i. Investigational devices**

N/A

ii. Investigational drugs

N/A

iii. Commercially available drugs, biologics, reagents or chemicals

Most common adverse reactions ($\geq 2\%$) are: fatigue, diarrhea, neutropenia, asthenia, anemia, peripheral neuropathy, leukopenia, dyspepsia, urinary tract infection, pain in extremity.

iv. Procedures

No procedures will be performed.

v. Radioisotopes/radiation-producing machines

N/A

vi. Physical well-being

No impact.

vii. Psychological well-being

No impact.

viii. Economic well-being

No impact.

ix. Social well-being

<Enter text or No impact. "NA">

x. Overall evaluation of risk

Low risk.

b. International Research Risk Procedures

N/A

c. Procedures to Minimize Risk

Patients will be screened for history of allergy or hypersensitivity to fosaprepitant.

d. Study Conclusion

Study will terminate when either 50 participants have been enrolled, or when results are deemed significant enough by principle investigator.

e. Data Safety Monitoring Plan (DSMC)

i. Data and/or events subject to review

According to section B1 of the data and safety monitoring form, we don't believe a DSMP is required for this study since it carries minimal risk.

ii. Person(s) responsible for Data and Safety Monitoring

Protocol Director

iii. Frequency of DSMB meetings

N/A

iv. Specific triggers or stopping rules

N/A

v. DSMB Reporting

N/A

vi. Will the Protocol Director be the only monitoring entity? (Y/N)

Yes

vii. Will a board, committee, or safety monitor be responsible for study monitoring? (Y/N)

No

f. Risks to Special Populations

N/A

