2. STUDY PROCEDURES

a. Procedures

On the day of surgery the patient will be consented in the preoperative area. We regularly use fosaprepitant in surgical patients undergoing procedures under general anesthesia with intraoperative neuromonitoring.

The patient will receive a single dose of 150 mg intravenous fosaprepitant after general anesthesia has been induced as prepared by pharmacy. Intraoperative neuromonitoring signals will be monitored for any changes during and after the administration of fosaprepitant.

The patient's intraoperative anesthetic management will be that typically utilized for surgical procedures with intraoperative neuromonitoring.

b. Procedure Risks

Using fosaprepitant in the operating room is widely used in the United States and is generally considered safe. This study will no withhold medication used to treat post-operative nausea and vomiting, rather, it seeks to determine if utilizing this very safe and effective medication during surgical procedures under general anesthesia with intraoperative neuromonitoring will alter or change intraoperative neuromonitoring signals due to the mechanism of action of the drug.

c. Use of Deception in the Study

No deception will be used.

d. Use of Audio and Video Recordings

No audio or video will be recorded.

e. Alternative Procedures or Courses of Treatment

At this point the use of fosaprepitant during surgery is at the discretion of the anesthesiologist. The effect of this medication on intraoperative neuromonitoring signals in patients having surgery under general anesthesia is not understood. No standard treatment is being withheld.

f. Will it be possible to continue the more (most) appropriate therapy for the participant(s) after the conclusion of the study?

After surgery the primary surgery team is free to utilize any nausea and vomiting control scheme they would like to use.

g. Study Endpoint(s)

Our study endpoint is whether a single dose of fosaprepitant at the start of surgery in patients having surgery under general anesthesia with intraoperative neuromonitoring causes any change in intraoperative neuromonitoring signals, and to quantify any such changes.

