10. BENEFITS

This study seeks to determine if fosaprepitant alters intraoperative neuromonitoring signals during general anesthesia. If it is found that this medication does alter intraoperative

neuromonitoring signals, it would be helpful to avoid administration of this medication during parts of the surgical procedure where changes in the intraoperative neuromonitoring signals could be mistakenly attributed to the surgical procedure causing neurological damage.

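### Section 9.d lets the investigator end the study once the results look significant enough, with no criterion, look schedule or error control

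*Protocol*

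**What the plan says.** Protocol Section 9.d (Study Conclusion) gives two ways for the study to end: "Study will terminate when either 50 participants have been enrolled, or when results are deemed significant enough by principle investigator". The first limb matches Section 8.a: "The total number of participants expected to enroll is 50". The second limb depends on the results and on one person's judgement.

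The only stated endpoint, in Section 2.g, is whether a single dose "causes any change in intraoperative neuromonitoring signals, and to quantify any such changes". It therefore has a detection part and an estimation part. The design in Section 2.a is one dosed group without a concurrent control: "Intraoperative neuromonitoring signals will be monitored for any changes during and after the administration of fosaprepitant".

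No other section defines or limits the second limb. Section 9.e makes the Protocol Director the only monitoring entity, with no board or committee. The item "iv. Specific triggers or stopping rules" in 9.e.iv is marked not applicable. That entry belongs to safety monitoring, so it is not treated here as contradicting 9.d, but it adds no limit either.

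**The concern.** A study that may stop whenever the accumulating result looks good enough has more than one chance to declare a finding, and it tends to stop when chance has made the effect look large. With no true change, this can raise the probability of declaring one. With a true change, the average estimate moves away from zero. An early stop also leaves fewer patients and a wider interval, which works against the aim of quantifying the change.

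The result has a stated use. Section 10 says that, if the drug alters the signals, "it would be helpful to avoid administration of this medication during parts of the surgical procedure". A false or exaggerated change would feed into that advice. Because every participant receives the drug, no comparison group would help expose a chance finding.

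**Working it through.** **What the protocol gives.** Maximum n = 50 (8.a and 9.d), one group with within-patient observation (2.a), and the stopping sentence (9.d). It states no alpha, test, effect size, SD or look schedule and no derivation of 50, so there is no stated figure to reproduce. Everything below is an assumed illustration.

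**Reading 1: stop on statistical significance.** Assume that within-patient change is normal with SD 1. At each look of size n, compute T = mean/(s/√n). Stop at the first look with |T| > t(0.975, n−1); otherwise continue to 50. Results are from 200,000 simulated trials per scenario. Mean estimates are over all trials, significant or not, so they show bias from stopping and not from selecting significant results.

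| Looks | False-positive rate | Mean estimate, true 0.2 SD | Mean estimate, true 0.3 SD | Mean n, true 0.3 SD | 95% CI coverage, no effect |
|---|---|---|---|---|---|
| 50 only | 5.0% | 0.200 | 0.300 | 50 | 95.0% |
| 25, 50 | 8.3% | 0.223 | 0.333 | 42.5 | 91.7% |
| Every 10 | 14.5% | 0.257 | 0.379 | 36.0 | 85.5% |
| Every 5 from the 10th | 17.2% | 0.266 | 0.388 | 33.8 | 82.8% |
| Every patient from the 10th | 22.3% | 0.278 | 0.399 | 30.9 | 77.7% |
| Every patient from the 5th | 27.3% | 0.300 | 0.432 | 28.6 | 72.7% |

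- False positives: 8.3/5.0 ≈ 1.7-fold up to 27.3/5.0 ≈ 5.5-fold.
- Bias at 0.2 SD: 0.223/0.200 is about +11% with one extra look; 0.257/0.200 to 0.300/0.200 is +28% to +50% with five or more.
- Bias at 0.3 SD: 0.333/0.300 = +11%; 0.379/0.300 to 0.432/0.300 is +26% to +44%.
- Coverage at a true 0.2 or 0.3 SD stays between 92% and 95%. There the main harm is bias and lost precision.

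**Larger true effect.** At a true 0.8 SD under the same rule, the mean estimate is 0.807 with one extra look (+1%), 0.848 to 0.864 with repeated looks from the 10th patient (+6% to +8%), and 0.916 when looking after every patient from the 5th (+14%). Relative bias shrinks as the true change grows.

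**Reading 2: stop on a change judged large enough.** Assume looks every 5 patients from the 10th, a stop if the observed mean change exceeds a threshold in either direction, then one 5% test.

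- Threshold 0.8 SD: false-positive rate 5.8%, or 5.8/5.0 ≈ 1.2-fold. Mean estimate 0.217 at a true 0.2 SD (about +9%) and 0.333 at a true 0.3 SD (+11%).
- Threshold 0.5 SD: false-positive rate 9.0%. Running the same simulation for the estimate gives about 0.270 at a true 0.2 SD (+35%) and 0.397 at a true 0.3 SD (+32%).

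**Precision.** The 95% half-width in SD units is t(0.975, n−1)/√n: 2.010/7.071 = 0.28 at n = 50, 2.064/5 = 0.41 at n = 25, and 2.262/3.162 = 0.72 at n = 10.

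**The case against.** The strongest reply is that the word significant in 9.d need not mean p<0.05. It may mean large enough to matter, and the protocol names no test. That stands as a limit on the size. The table covers one reading only; under the other, the false-positive rate may be as low as about 6%. It does not remove the defect. Stopping on a large observed change is still stopping on the result, and it still pushes the estimate away from zero, by about as much as frequent significance looks when the threshold is 0.5 SD. The uncertainty over which reading applies also means that nobody could check whether the rule was followed.

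A second reply is that relative bias is modest when the true change is large. That is correct, and the documents give no expected effect, so the +28% to +50% range should not be taken as general.

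A third is that an analysis plan not shown might set a boundary. A protocol silent on interim looks could be completed that way. This one is not silent: it makes discretion the trigger and refers to no plan.

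Finally, this is a single dose of a commercial drug in a study rated low risk, and 50 is a cap. This limits the harm to participants, but it does not protect the validity of the only endpoint.

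**Conclusion.** The concern holds. Section 9.d fixes a discretionary, results-driven stop, and nothing else in the protocol limits it. Depending on the looks taken, it can raise the false-positive rate and exaggerate the estimated change, so it reaches both parts of the endpoint in 2.g.

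The size cannot be derived from the protocol. Under the assumptions shown, the false-positive rate runs from about 6% (a rare stop on a large observed change) to 27% (testing after every patient from the 5th). Bias depends on the true change: at 0.2 to 0.3 SD it is about 10% under the mildest rules and up to 50% under the most frequent looks. The existence of the problem does not depend on these figures. It should be corrected before any results-based decision to stop, because error incurred through unplanned looks cannot be removed afterwards.

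**What to change.** Delete the second limb of the sentence in 9.d, that is, everything after the first condition, so that the study ends when 50 participants have been enrolled and is analysed once. This is a one-sentence amendment. It needs no participants beyond those planned, and the only thing lost is the option of an ad hoc early stop. Of the options considered, only this removes both the error inflation and the stopping bias.

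If an early stop is really wanted, write it as a prespecified rule. One example, assuming a single continuous endpoint and a two-sided 5% test, is one look at 25 participants, stopping only if p<0.003, with the final test at p<0.049.

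- **Overall error:** the critical values are 2.968 and 1.969, with correlation √(25/50) = 0.707 between the two statistics. This gives 0.04998 by bivariate normal calculation and about 0.050 by t-test simulation.
- **Power at a true 0.3 SD:** 54.7%, against 54.5% for a fixed 50.
- **Residual bias:** mean estimates of 0.204 at a true 0.2 SD and 0.310 at a true 0.3 SD, about 2% to 3%. A bias-adjusted estimate should therefore be reported after an early stop.

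The rule should also say who looks at the data and who decides.

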1. PURPOSE OF THE STUDY

a. Brief Summary

The purpose of this study is to determine if intravenous fosaprepitant can interfere with nervous system monitoring signals in patients having surgery under general anesthesia. Fosaprepitant is a drug commonly used to prevent post-operative nausea and vomiting, and works by inhibiting "substance P", which is found in the brain and spinal cord. Theoretically, fosaprepitant could interfere with nervous system recordings because of its effect on substance P, but it is not known if this actually occurs. The drug will be given after the patient has been anesthetized but before surgical incision so that if there are any changes on the intraoperative neuromonitoring signals they can only be attributed to fosaprepitant.

b. Objectives

If fosaprepitant alters intraoperative neuromonitoring signals during surgical procedures under general anesthesia, it would be important because anesthesiologist's who administer this drug would want to give it at the beginning of surgery when changes in intraoperative neuromonitoring signals would be unlikely to mean that these changes were due to surgical damage to the nervous system.

c. Rationale for Research in Humans

We are specifically interested in evaluating if fosaprepitant alters intraoperative neuromonitoring signals in human patients having surgery under general anesthesia.

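### Does the risk section need a safety-review trigger because it enters no physical impact and names no event for review?

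*Protocol*

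**What the plan says.** Four parts of the protocol bear on this.

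- **Possible interference.** Section 1.a: "Theoretically, fosaprepitant could interfere with nervous system recordings because of its effect on substance P", with the caveat that it is unknown whether this happens. Section 2.e: "The effect of this medication on intraoperative neuromonitoring signals in patients having surgery under general anesthesia is not understood". Section 10 adds that a drug-related change might be misread as surgical injury.
- **Timing and observation.** Section 1.a: "The drug will be given after the patient has been anesthetized but before surgical incision". Section 2.a places the dose "after general anesthesia has been induced as prepared by pharmacy" and adds: "Intraoperative neuromonitoring signals will be monitored for any changes during and after the administration of fosaprepitant". Section 2.g describes "a single dose of fosaprepitant at the start of surgery".
- **Risk entries.** Section 9.a.iii lists, at 2% or more: "fatigue, diarrhea, neutropenia, asthenia, anemia, peripheral neuropathy, leukopenia, dyspepsia, urinary tract infection, pain in extremity". Section 9.a.vi enters no impact for physical well-being, and 9.a.x gives low risk overall. Section 9.c names screening for allergy or hypersensitivity.
- **Monitoring.** In 9.e.i the investigators cite a section of a data and safety monitoring form and say they do not believe a "DSMP is required for this study since it carries minimal risk". Sections 9.e.ii and 9.e.vi make the Protocol Director the sole monitor. Section 9.e.iv enters not-applicable for triggers or stopping rules. Section 9.d ends the study at 50 participants, or sooner if the principal investigator judges the results significant enough.

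**The concern.** Read alone, section 9 seems to belong to a different study. It lists ten physical reactions and then enters no physical impact. The effect that motivates the trial, altered neuromonitoring, is missing from the list of risks, and the minimization paragraph deals only with allergy. The heading for events subject to review names none.

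If a participant's signals were lost, or stayed altered into the operation, the surgical team could be misled about neurological injury, which is the consequence section 10 describes. Nothing in section 9 would oblige the Protocol Director to look at that case before the next participant was dosed.

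The pre-incision timing, which is the main protection against misattribution, is spelled out only in the summary. The procedures and endpoint sections use looser words, which raises the question whether the protocol is consistent about when the drug is given.

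**Working it through.** The question is mainly textual. There is no plan figure to reproduce, because the protocol gives no signal-change rate, duration, power or error rate. I compared the passages point by point.

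**1. Physical impact (9.a.iii against 9.a.vi).** Taken literally, the two entries conflict. The one with content is 9.a.iii, and it discloses the reactions. The 9.a.vi entry sits in a run of template headings (physical, psychological, economic, social), and the social one still carries its unfilled prompt. This is a form-filling slip. Correcting it changes no eligibility rule, dose, measurement or analysis.

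**2. Signal interference missing from section 9.** It is missing there, but it is not hidden. It is stated in 1.a, 2.e and 10. Section 2.b, which is headed as procedure risks, says the study seeks to learn whether the drug changes the signals. It is also the endpoint in 2.g.

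**3. Dose timing.** The three statements are:

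| Section | Lower limit | Upper limit |
|---|---|---|
| 1.a | after anesthesia | before incision |
| 2.a | after induction | none stated |
| 2.g | start of surgery | none stated |

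A dose after induction and before incision meets all three. That one of the three mentions incision counts repetition; it does not show a contradiction.

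**4. Risk screening.** Section 9.c names allergy only, but 8.h.ii excludes anyone with a contraindication to the drug, and 8.i has study anesthesiologists review the chart. Neither addresses signals. Both show that screening is wider than 9.c suggests.

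**5. Review and stopping.** A responsible monitor is named (9.e.ii). Signals are watched during and after the dose (2.a). Because signal change is the only endpoint, the results that may end the study early under 9.d are signal results. What is missing is a *mandatory* case review. Whether 9.d is a sound rule for inference is a separate matter.

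**6. What can be counted.** Suppose each listed reaction occurred at exactly the 2% floor in this setting, which the protocol does not state. Then:

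- expected cases of one reaction: 50 × 0.02 = 1.0
- chance of at least one: 1 − 0.98^50 = 0.636

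At half that rate:

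- expected cases: 50 × 0.01 = 0.5
- chance of at least one: 1 − 0.99^50 = 0.395

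These figures show that no impact is not literally accurate. They say nothing about lost or persistent signal changes. Nor do they measure risk added by the study, since 2.a describes regular use of the drug in these patients and 2.e leaves its use to the anesthesiologist.

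**The case for a change.** The strongest case for a change is that risk statements and oversight belong in the protocol, so no analysis plan would supply them. A study that thinks an effect important enough to investigate should list it as a foreseeable risk and say who looks at a bad instance of it. Pre-incision dosing is justified in 1.a by attribution, not protection, and it does not deal with a change that outlasts the start of surgery. The remedy would be cheap: some wording, and a case review by a monitor already named.

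Part of this stands. Section 9.a.vi is wrong as written, section 9 is thinner than sections 1, 2 and 10, and a persistent change is not addressed.

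The step from there to a required change does not stand. The wording corrections leave the trial exactly as it is. The review trigger could not be *any change*, because that is the endpoint. It would need a threshold for material and persistent change, for which the protocol offers no basis, and it might pause enrolment. Whether that is worthwhile for a formulary drug (8.l) already used locally is a judgment on which reasonable teams differ. The protocol gives its reason for having none, minimal risk, and refers to a form that is not at hand, so the determination cannot be shown to be wrong from this document.

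**Conclusion.** No change to the plan is called for. Two things are established: a clerical inconsistency between 9.a.iii (ten reactions) and 9.a.vi, and a risk section that does not repeat the possible interference described elsewhere in the protocol. Neither affects who is enrolled, what is given, what is measured or what can be concluded. The timing statements do not conflict. The lack of a mandatory review trigger is a trade-off in a study of 50 with a named monitor, observed signals and a discretionary early stop.

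The probability and duration of a serious signal change remain unquantified, because the protocol gives neither. The conclusion rests on three things taken from the text: the dose is given before incision as 1.a says, signals are watched as 2.a says, and the drug is already in regular local use as 2.a says. If the before-incision timing in 1.a were not followed in practice, the matter would deserve another look.
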